### 3.2 Randomization and Blinding

At each study center, all subjects included in the Safety Study part (open label study part) will receive E4 20 mg (oral, once daily). Blinding is not applicable for this part of the trial.

### 3.3 Study Treatments and Assessments

After inclusion in the safety study part, the trial medication will be dispensed (see Section 9.4 in protocol) and subjects will take trial medication (20 mg E4, oral, once daily) on the day of treatment allocation visit (day 1 of week 1) and during the treatment period (Visit 1 - Visit 6). Subjects will be instructed to take the trial medication at approximately the same time each day. If a subject misses a dose, she will be instructed to take the dose as soon as she remembers. It is acceptable to take a dose up to 12 hours late. If taken more than 12 hours late the subjects will be instructed to omit dosing for that day and continue with the next dose as usual.

An overview of time windows for each visit is presented in [Appendix1](#); detailed description of procedures and assessments to be conducted during this study is summarized in [Appendix2](#).

---

**4 SAMPLE SIZE AND POWER**

The target number of subjects to be included in the Safety Study part is approximately 400.

Enrollment will stop when the minimum required number of subjects in each study group and study part have been enrolled. The number of subjects has been selected to fulfill the requirement stated in ICH E1 guideline (CPMP/ICH/375/95) regarding number of subjects exposed to the drug for safety assessments.

---

## 5 ANALYSIS POPULATIONS

### 5.1 Enrolled Set

Enrolled Set will include all subjects who sign the ICF.

### 5.2 Included Set

The Included Set will include all subjects allocated to the Safety Study part treatment arm. This will be the main analysis set for the disposition table and all the listings for the Safety study part.

### 5.3 Safety Analysis Set

The Safety Analysis Set will include all subjects who receive at least one dose of study drug. The Safety Analysis Set will be used for all analyses of efficacy, safety, tolerability, and background characteristics.

### 5.4 Per-Protocol Set

The Per-Protocol (PP) Set will include all subjects who receive at least one dose of study drug and who do not have major protocol deviations. The major protocol deviations will be defined at the time of the evaluability assessment between the database soft lock and hard lock. The PP Set will be used for efficacy sensitivity analyses.

### 5.5 Protocol Deviations and Exclusions from Analysis Sets

A protocol deviation is defined as an instance of failure to follow, intentionally or unintentionally, the requirements of the protocol procedures or requirements.

All deviations and exclusions of subjects from analysis sets will be identified at a Classification Meeting just prior the database lock and the final analysis, through clinical review input, provided by Sponsor, and using the Protocol Deviation Logs, provided by ICON clinical trial management system (CTMS).

Further, deviations from protocol will be classified as major or minor.

## 6 STATISTICAL CONSIDERATIONS AND ANALYSIS

### 6.1 Derived Variables

The below table ([Table 1](#)) provides the list of derived variables for demographic and baseline characteristics, various duration derivations, baseline derivations and other important derivations applicable for this study.

**Table 1: Derived Variables**

Variables	Formula																								
Demographic and Baseline Characteristics																									
Body mass index (BMI) (kg/m  )	weight (kg)/[height (m)] 																								
Study Treatment																									
Treatment Start Date	The date of first dose of study drug.																								
Treatment Stop Date	The date of last dose of study drug.																								
Duration of exposure (Days)	(Treatment Stop Date – Treatment Start Date) + 1																								
Treatment compliance (%)	100 x [(total number of tablets dispensed) – (total number of tablets returned)]/(duration of exposure in days)																								
Study Day	Prior to Treatment Start Date: Date of interest – Treatment Start Date  On or after Treatment Start Date: Date of interest – Treatment Start Date + 1																								
Study Week	
Study Week is defined as follows for the first 7 weeks
 
  
 Week	Start (Study Day)	End (Study Day)	
   
 1	1	7	
 
 2	8	14	
 
 3	15	21	
 
 4	22	28	
 
 5	29	35	
 
 6	36	42	
 
 7	43	49	
  
	Week	Start (Study Day)	End (Study Day)	1	1	7	2	8	14	3	15	21	4	22	28	5	29	35	6	36	42	7	43	49
Week	Start (Study Day)	End (Study Day)																							
1	1	7																							
2	8	14																							
3	15	21																							
4	22	28																							
5	29	35																							
6	36	42																							
7	43	49																							

Study Cycle	28-day period starting from Treatment Start Day
Adverse Events	
Adverse Event (AE) Start Day	Prior to Treatment Start Date: AE start date – Treatment Start Date  On or after Treatment Start Date: AE Start Date – Treatment Start Date + 1
AE Stop Day	Prior to Treatment Start Date: AE stop date – Treatment Start Date  On or after Treatment Start Date: AE stop date – Treatment Start Date + 1
AE Duration (Days)	(AE Stop Date – AE Start Date) + 1
TEAE	AE Start Date known: TEAE if AE Start Date on or after Treatment Start Date and AE Start Date is before the date of the last visit where last visit is defined as end of treatment, early discontinuation or follow up visit (for NH subjects).  AE Start Date unknown: TEAE if AE Stop Date is on or after Treatment Start Date.
Baseline	
Baseline	Unless otherwise noted, Baseline is defined as the last non-missing value, including results from repeated and unscheduled measurements, prior to Treatment Start Date.
Change from Baseline	Date of interest – Baseline
Other	
TS	TS is the percentage of subjects in each category in CGI questionnaire (very much improved, much improved, minimally improved, no change, minimally worse, much worse, and very much worse) which will be presented at week 4, week 12 and week 52 for the different treatment group.

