10.1.6.6. Visit 6: End of Trial/Early Termination Visit (week 53 or earlier)

Subjects will return to the trial site in week 53 for Visit 6. This will be the EoT and follow-up procedures will be performed. Subjects will take their last daily dose of the trial medication on the evening before the EoT visit.

For subjects who terminate early every reasonable effort should be made by the investigator to complete the final assessment procedures as specified in this section (see also Section 8.3). In case of early termination treatment may have been stopped earlier.

The following observations/procedures are to be performed and checked at Visit 6:

- Physical examination
- Gynecological examination
- Breast examination
- Digitalized mammography (in case of early termination, mammography may only be performed if subjects was treated for at least 12 weeks and last mammography was taken at least 9 months earlier)
- Vital signs
- 12-lead ECG
- Endometrial biopsy if the subject has at least completed 12 weeks of treatment (for non-hysterectomized women only)
- TVUS (for women who still have uterus and/or ovaries)
- MENQOL and CGI questionnaires
- Fasted blood sampling for:
 - Routine hematology, chemistry
 - Lipid metabolism
 - Glucose metabolism
 - Additional optional analysis
- Review of returned trial medication/drug accountability
- Dispense trial medication (P4 200 mg for non-hysterectomized subjects only)
- Record prior/concomitant medication
- Record AEs
- Complete end of trial form (hysterectomized subjects only)

For hysterectomized subjects: after completion of the Visit 6 procedures in the Safety Study part, the subject has completed the trial.

For non-hysterectomized subjects: after completion of Visit 6 procedures the subjects will start treatment with 200 mg P4 once daily for 14 days. Subjects should take the progestin medication as per investigator's instructions. Subjects are instructed to record the vaginal bleeding events and P4 intake in the diary. Subjects will return to the clinic approximately 10 days after completion of the progestin treatment for the endometrial safety follow-up visit (Visit 7).

10.1.6.7. Visit 7: Non-hysterectomized Subjects Only: Endometrial Safety Follow-up Visit (week 55/56 or earlier)

The following observations/procedures are to be performed and checked at Visit 7:

- TVUS
- Return of diary
- Review of diary
- Review returned unused medication/drug accountability
- Record concomitant medication
- Record AEs

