10.4.1. Treatment Emergent Adverse Events

- All AEs that occur during the trial after the subject has signed the informed consent are to be documented in the eCRF, regardless of whether they are reported by the subject, elicited by Investigator questioning, detected through physical examination, or by other means.

For adverse events of special interest see Section 10.6.

As far as possible, each AE is described by:

- Duration (start and end dates);
- Start/end of trial medication;
- Severity grade (mild, moderate, severe);
- Investigation causality (relationship to the trial product);
- Action(s) taken (concomitant medication, change of trial medication etc.) including start and end of respective action;
- Concomitant diseases and respective medication in general;
- Start, end and dosage of rescue medication;
- Outcome.

Definition of terms:

AE

An AE is any untoward medical occurrence (change in anatomical, physiological, or metabolic function) in a subject, which does not necessarily have any causal relationship with the product under investigation. An AE may be an exacerbation of a pre-existing medical condition that was present before the subject was assigned to a treatment group.

TEAE

Treatment emergent AEs (TEAEs) are those AEs occurring from time point of first ingestion of investigational product until last visit or any event already present that worsens in either intensity or frequency following exposure to the treatment.

SAE or TESAE

An SAE is any untoward medical occurrence that at any dose:

- Results in death;
- Is life-threatening (Note: the term “life-threatening” refers to an event in which the subject is at risk of death at the time of the event; it does not refer to an event which hypothetically may cause death if it is more severe);
- Requires subject hospitalization or prolongation of existing hospitalization (for the purpose of this trial, a hospitalization is defined as a hospital stay of at least 8 hours and/or an overnight stay);
- Results in persistent or significant disability/incapacity;
- Is a congenital anomaly/birth defect;
- Other medically important condition.

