If an AE occurs, appropriate diagnostic and therapeutic measures are to be taken and the trial product must be discontinued if appropriate. Follow up evaluations of the subject are to be performed until the subject recovers or until the clinical Investigator considers the situation to be no longer clinically significant, at the maximum of 30 days following completion of the trial.

If clinically significant laboratory abnormalities appear at the final visit, appropriate additional tests may be performed to clarify the nature of any clinically significant laboratory abnormalities that occur.

AEs are monitored and registered on the AE form of the eCRF at each visit. The Investigator must make a determination of relatedness, seriousness, and intensity. All AEs during the study will be documented in the subject's medical record. This information will then be transcribed on the AEs form of the eCRF by designated study personnel. Required information includes a description of the event, date of onset, date of resolution, the outcome, the action taken to manage the AE, the impact on the study drug intake, as well as relatedness, seriousness and intensity. In the absence of a specific diagnosis, an individual AE form has to be filled in for each sign or symptom.

Persistent AEs will be entered once in the eCRF until they are resolved or if a new event has to be documented due to deterioration. These AEs will be carefully monitored; further details of monitoring of persistent AEs will be provided in the monitoring plan. If an AE is still not resolved at the end of the trial, this will be documented as ongoing.

For recurrent AEs, i.e., AEs of the same nature, but with a different date of onset, an individual AE form must be completed for each of them.

AEs occurring after the termination of the trial individually and/or of the trial in total are to be reported to the Sponsor even after the clinical trial has been finished if, in the judgment of the Investigator, there is an association between the event and the previous use of the product under investigation.

If the AE is classified as serious, Investigators or designated study site personnel must inform the appropriate CRO representatives of any SAEs that occur (whether or not related to the study drug) in the course of the study, within 24 hours of when he/she becomes aware of it.

All cases of VTE or arterial thromboembolism should be treated as SAE and reported in the same manner as SAEs.

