10.4.2. Physical and Gynecological and Breast Examination

A physical examination will be performed for each subject during the Screening Period and at the EoT (Visit 7 Efficacy Study part/Visit 6 Safety Study part).

This evaluation will include an examination of general appearance, head, eyes, ears, nose, throat, skin neck, lungs, breast, lymph nodes, abdomen, and the cardiovascular musculoskeletal and neurological systems.

A gynecological and breast examination will be performed for each subject during the Screening Period and at the EoT (Visit 7 Efficacy Study part/Visit 6 Safety Study part). This evaluation will include a manual pelvic and breast. Additional breast examinations will be performed after 6 months of treatment (Visit 5 Efficacy Study part/Visit 4 Safety Study part). Gynecological and breast examinations will be done by trained and experienced personnel as per to local regulations.

All abnormal findings in the physical, gynecological and breast examinations that are considered by the Investigator to be clinically significant will be recorded as AEs (Section 10.4.1).

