10.4.3. Vital Signs

Vital signs will include height, body weight, BMI, sitting systolic and diastolic BPs, and heart rate. BP will be taken at all visits; height will only be measured during screening, weight will

only be measured at during screening and at the EoT visit. The same equipment (e.g., scale) should be used for all measurements. BMI will be calculated from the subjects height and weight using the formula $BMI = \text{kg}/\text{m}^2$; where kg is the body weight in kilograms and m^2 is the body height in meters squared. BP measurements will be made using a sphygmomanometer with an appropriate cuff size for the individual subject. Measurements will be taken while the subject is seated after at least 5 minutes at rest. Other procedures should not be performed during the time of the blood pressure and pulse rate measurements. BP measurements at screening may be repeated if values are outside the inclusion criteria after sitting for an additional 5 to 10 minutes. The last reading will be used for eligibility.

All abnormal findings in vital signs that are considered by the Investigator to be clinically significant will be recorded as AEs (Section 10.4.1).

10.4.4. **Electrocardiogram**

A 12-lead ECG will be recorded for each subject during screening and at the EoT Visit (Visit 7 Efficacy Study part/Visit 6 Safety Study part). ECGs will be read locally. The ECG interpretation scheme will include the analysis of the morphology, rhythm, conduction, ST segment, PR, QRS, QT and QTc (according to QTcFrid) intervals, T waves, U waves and the presence or absence of any pathological changes.

All abnormal findings in ECG that are considered by the Investigator to be clinically significant will be recorded as AEs (Section 10.4.1).

10.4.5. **Routine Clinical Laboratory Tests**

Methods for blood collection, processing, and shipment are described in instructional materials provided to investigational sites. Leftover blood samples will be retained after this trial for optional additional analyses in the context of this program or any further research on E4; details of the sample retention for future research as well as subject's rights in regard to these samples are presented in the ICF.

Blood samples for the assessments lipids and glucose need to be taken in **fasting** conditions (at least 8 hours fast).

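### SAP Table 1 closes the TEAE window the day before the last visit, while protocol 10.4.1 most naturally includes that day, and SAP section 8 does not declare the difference (minor)

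*SAP*

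**What the plan says.** SAP section 6.1, Table 1, gives the derivation for a known start date: "TEAE if AE Start Date on or after Treatment Start Date and AE Start Date is before the date of the last visit". Last visit there means the end-of-treatment visit, the early-discontinuation visit or, for non-hysterectomized women, the follow-up visit. For an unknown start date the same row has no upper limit: "AE Start Date unknown: TEAE if AE Stop Date is on or after Treatment Start Date".

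Protocol 10.4.1 defines TEAEs as "AEs occurring from time point of first ingestion of investigational product until last visit", and adds pre-existing events that worsen.

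SAP 7.7.1.1 lists all adverse events but summarizes only TEAEs, and it refers back to section 6.1 for the definition. TEAE frequency is the first safety endpoint under the primary objective in SAP 2.1. SAP section 8 lists three departures from the protocol, all about analysis sets (Endometrial Safety Analysis Set, ITT, mITT).

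**The concern.** Read literally, the SAP rule drops any event whose onset is dated to the last visit. For hysterectomized women that visit is Visit 6, after which they leave the trial: "For hysterectomized subjects: after completion of the Visit 6 procedures in the Safety Study part, the subject has completed the trial". The same applies to a non-hysterectomized woman who never attends Visit 7.

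Visit 6 is not an ordinary day. It holds the only scheduled post-baseline physical examination, gynecological examination and ECG, and clinically significant findings from these become adverse events. A rule that stops one day short of it can only reduce the reported TEAE frequency, and it does so without being declared as a change from the protocol.

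**Working it through.** The plan states no figure to reproduce. The check is a comparison of date boundaries, followed by simple arithmetic on size.

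**1. Boundary comparison.** Let L be the date of the last visit.

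| Known AE start date | SAP Table 1 | Protocol, L included | Protocol, L excluded |
|---|---|---|---|
| L − 1 | TEAE | TEAE | TEAE |
| L | not a TEAE | TEAE | not a TEAE |
| L + 1 | not a TEAE | not a TEAE | not a TEAE |

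The only possible gap is the day L itself, and it exists only if the protocol wording includes L.

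**2. Does the protocol include L?** The word *until* does not settle it. The surrounding text favours inclusion:
- Protocol 10.4.1: "AEs are monitored and registered on the AE form of the eCRF at each visit".
- Protocol 10.1.6.6 lists recording of adverse events among the Visit 6 procedures.
- Protocol 10.4.1 expects findings to arise on that day: "If clinically significant laboratory abnormalities appear at the final visit, appropriate additional tests may be performed".

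**3. Is it declared or explained elsewhere?** No. Section 8 is silent, and no other SAP section restores the day. The SAP is written against protocol version 7.1 rather than 8.0, but that does not explain the difference: the protocol's summaries of Amendments 6.1 and 7 show only endometrial follow-up text changing in 10.4.1.

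**4. What falls on L?**
- Hysterectomized women, and non-hysterectomized women without Visit 7: L is the end-of-treatment or early-discontinuation visit. Protocol 10.4.2 covers "All abnormal findings in the physical, gynecological and breast examinations that are considered by the Investigator to be clinically significant" and has them recorded as adverse events. Protocol 10.4.4 states: "All abnormal findings in ECG that are considered by the Investigator to be clinically significant will be recorded as AEs".
- Non-hysterectomized women who attend Visit 7: L is Visit 7, so an event dated to Visit 6 remains a TEAE.
- Laboratory results: hematology and chemistry are also measured after baseline only at Visit 6. However, protocol 10.4.5 prefers recording the underlying sign, symptom or diagnosis to recording the value, and samples go to a central laboratory. A laboratory finding is affected only if it is recorded as an adverse event or diagnosis dated to L.

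**5. Size.**
- Hysterectomized completer, Visit 6 window Day 365 to 371 (SAP Table 5). With Visit 6 on Day 365 the SAP window is Days 1–364 instead of 1–365. Share lost: 1/365 = 0.274%. At Day 371: 1/371 = 0.270%.
- Non-hysterectomized completer with Visit 7 on Day 392: Days 1–391 instead of 1–392. Share lost: 1/392 = 0.255%.
- Overall TEAE frequency, planned N of about 400: a woman changes it only if she has no other TEAE. Each such woman moves it by 1/400 = 0.25 percentage points, or by 1/200 = 0.5 points within the hysterectomized column of the overview table (about 200 women). Moving the overall figure by one point would take four such women (4/400).
- The number of such women cannot be derived from the documents.

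**The case against.** The strongest reply is that no contradiction has been shown. *Until* may exclude its endpoint, and registering events at each visit may simply mean collecting those that occurred since the previous one. This stands in part: the SAP rule is a permissible reading, though the less natural one. If it was intended, it should be stated.

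Second, in the Safety Study part the last dose is taken the evening before the end-of-treatment visit (protocol 10.1.6.6), so no planned dosing day is lost. That is true, but it does not justify the limit. The SAP window is not restricted to dosing days: for non-hysterectomized women it runs on to just before Visit 7.

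Third, the protocol asks for date of onset, not of detection. A condition found at Visit 6 may carry an earlier date and be counted. This stands and limits the number of events affected.

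Fourth, the information is visible elsewhere. All adverse events and all SAEs are listed with TEAE flags (SAP 7.7.1.1). Shift tables cover laboratory, physical examination, ECG and gynecological results (SAP 7.7.1.2, 7.7.1.4, 7.7.1.5, 7.7.1.7). The analysis is single-arm and descriptive with no formal test (SAP 7.1). This stands and is the main reason for the low rating.

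A reader might also infer more than the documents support:
- *That laboratory abnormalities at the final visit drop out of the safety results.* They do not. SAP 7.7.1.2 summarizes samples taken up to 30 days after last exposure, and protocol 10.4.5 steers away from recording the value itself as an event. That 30-day rule governs a different data type and is not evidence of conflict with the TEAE rule.
- *That the open-ended rule for unknown start dates contradicts the strict rule for known dates.* An unknown date cannot be tested against an upper limit, so counting such an event is a cautious default.

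**Conclusion.** The point holds as a minor correction. A stated derivation for the first primary endpoint drops events dated to the last visit, which departs from the natural reading of protocol 10.4.1 and is not declared in SAP section 8. The effect is one calendar day per woman, in one direction only (fewer TEAEs), and is probably small. A claim that TEAE frequency is materially understated would go beyond the documents.

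The conclusion rests on two assumptions: that *until last visit* includes that day, and that at least some findings made at the end-of-treatment or early-discontinuation visit are given that date as onset. If the first fails, what remains is a request to state the rule explicitly. If the second fails for examination and ECG findings, the practical effect is limited to events that happen to begin that day.

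One adjacent discrepancy should be settled at the same time but adds nothing to the rating. AESI collection ends at the end-of-treatment visit in protocol 10.6 and at the follow-up visit in SAP 7.7.1.1. Because the SAP treats AESIs as a subset of TEAEs, an AESI starting on the follow-up visit date would be collected and yet fail the TEAE rule.

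**What to change.** In SAP Table 1, change the upper limit of the known-date TEAE rule from *before* to *on or before* the date of the last visit. If the strict limit is intended, list and justify it in SAP section 8.

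Separately, reconcile the end of AESI collection between protocol 10.6 and SAP 7.7.1.1.

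The cost is one phrase in a derivation, the matching program line, and one reconciled date. The TEAE change needs no new data, and reported TEAE counts can only stay the same or rise slightly.

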8. SUBJECT SELECTION AND DISCONTINUATION/WITHDRAWAL OF SUBJECTS

8.1. Source and Number

This will be a multicenter trial performed in multiple study sites in the United States of America and Canada. Subjects will be recruited by the investigator from his/her patients or will be recruited by recruitment campaigns. Subjects must seek treatment for the relief of menopausal symptoms, or subject may already be treated for menopausal symptoms and willing to discontinue their current treatment.

All investigators must keep a record of subjects who were considered for enrollment and were consented, but were never enrolled e.g., subject screening log to address concerns over selection bias.

This trial will enroll a total of approximately 1,000 subjects; ~600 subjects ~200 per treatment arm) in the Efficacy Study part and ~400 subjects in the Safety Study part of the trial. Enrollment will stop when the minimum required number of subjects in each study group and study part is enrolled.

The number of completers after three months of treatment in the Efficacy Study part is anticipated to be around 435, anticipating a drop-out rate of 35% and 20% for non-hysterectomized and hysterectomized women, respectively. The number of completers after 12 months of treatment is anticipated to be ~300, anticipating a drop-out rate of 50% after one year of treatment.

The number of completers in Safety Study part after 12 months of treatment is expected to be ~200, anticipating a drop-out rate of 50%.

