8.3. Subject Discontinuation and Replacement Procedures

Subjects may withdraw their consent and may discontinue from trial treatment and assessments at any time and for any reason. Subjects are free to discontinue their participation in the trial, without prejudice to further treatment.

In addition, a subject may be withdrawn by the investigator or Sponsor in the case of emerging effects of such a nature that the risk/benefit ratio is unacceptable, in the case of poor compliance or protocol violation, if enrollment into the trial is inappropriate or for administrative and/or other safety reasons.

If a subject does not complete the trial for any reason (including investigator discretion), the reason and circumstances for the subject's early termination must be fully documented in the electronic case report form (eCRF). Possible reasons for a subject discontinuing participation in the trial are (non-exhaustive list):

- SAE(s) that endanger the health of subjects, making it ethically unacceptable to continue or any SAE(s) that the subject finds intolerable
- Deterioration of the subject's clinical condition(s) that requires appropriate therapy/treatment during the trial period as per Investigator's or Sponsor decision
- Endometrium biopsy showing a disordered proliferative pattern, hyperplasia or worse, requiring treatment with a progestin
- Endometrial safety findings that preclude further treatment of non-hysterectomized subjects
- Withdrawal of consent due to lack of efficacy
- Withdrawal of consent for another reason
- Non-compliance to trial protocol: VMS count compliance
- Non-compliance to trial protocol: study drug intake compliance
- Non-compliance to trial protocol: others
- Lost to follow up
- Death
- Other

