## **2 STUDY OBJECTIVES AND ENDPOINTS**

### **2.1 Primary Objective and Endpoint**

To evaluate the general safety of treatment with Estetrol (E4) 20 mg.

Safety endpoints for primary objective #1

- Frequency of Treatment Emergent Adverse Event (TEAE) (including Serious Adverse Events [SAEs])
- Frequency of changes in results in physical and gynecological examinations, vital signs, electrocardiogram (ECG), mammography, and breast examination at each measured time point
- Frequency of changes in routine clinical laboratory tests results (hematology and chemistry) at each measured time point

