#### If Year of AE Start Date is missing:

If the year of AE start is missing or AE Start Date is completely missing, then:

- No imputation will be done.

If the year of AE start is missing and AE Stop Date is not missing, then:

---

- If the AE Stop Date is before the Treatment Start Date then the AE should be considered as a pre-treatment AE.
- Otherwise, the AE will be considered as TEAE.

Imputation rules for missing or partial medication start/stop dates are defined below:

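### Read literally, the SAP's TEAE rule cannot be met by a dosed woman who has no end-of-treatment, early-discontinuation or follow-up visit: her dated AEs leave the numerator while she stays in the denominator

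*SAP*

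**What the plan says.** **TEAE, start date known (SAP 6.1, Table 1).** Two conditions must both hold. The AE starts on or after Treatment Start Date, and it starts "before the date of the last visit where last visit is defined as end of treatment, early discontinuation or follow up visit". No substitute date is offered when none of these visits took place.

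**TEAE, start date unknown (same table).** "AE Start Date unknown: TEAE if AE Stop Date is on or after Treatment Start Date". SAP 6.2.1.2 adds that nothing is imputed when the start year or the whole start date is missing. It then classifies such events by stop date only when a stop date is present.

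**Protocol 10.4.1.** TEAEs are those "occurring from time point of first ingestion of investigational product until last visit", with no limit on which visit counts as the last. The definition also includes pre-existing events that worsen on treatment.

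**Denominator (SAP 5.3).** "The Safety Analysis Set will include all subjects who receive at least one dose of study drug". The TEAE overview in SAP 7.7.1.1 takes its percentages from this set.

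**Endpoint (SAP 2.1).** TEAE frequency, including serious events, is the first of the three primary safety endpoints of the Safety Study part.

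**Leaving the trial (Protocol 8.3).** The listed reasons include "Lost to follow up" and death. The early termination visit is requested, but only where it can be achieved.

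**The concern.** The upper end of the TEAE window is tied to one of three named visits. A woman who attends Visits 2 and 3, reports AEs there and is never seen again has none of those dates, so the second condition has nothing to be compared with and cannot be satisfied. The same is true of a woman who dies on treatment: her fatal event can be precisely dated and still fail the rule.

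Such women are dosed, so they count in every TEAE percentage. The omission runs in one direction only, because events can be lost and none can be gained. It carries into every table built on the flag: all TEAEs, serious TEAEs, TEAEs leading to discontinuation or to death, and AESIs, which SAP 7.7.1.1 defines as a subset of TEAEs. The other two primary safety endpoints (examination and laboratory changes) do not use this rule.

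**Working it through.** **1. Is early discontinuation a visit or just a date?** Table 1 lists it as a kind of last visit. SAP 7.1 separates the early-discontinuation visit from the scheduled end-of-treatment visit by the discontinuation reason, and Tables 6 and 7 in Appendix 1 relabel Visit 6 accordingly. So Visit 6 has to have been attended; a recorded stop date alone does not meet the wording.

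**2. Is there a fallback elsewhere?** SAP 6.2.1.2 imputes AE start dates and medication dates, not the end of the TEAE window. The patient-years formula in 7.7.1.1 uses a cut-off date for ongoing subjects, but only for exposure time. Neither repairs Table 1.

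**3. The rule applied literally.** Condition: start ≥ treatment start AND start < last-visit date. A missing last-visit date was treated as the lowest value, which is how SAS orders missing values.

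| Woman | AE start days | Last-visit date | TEAEs counted | In denominator |
|---|---|---|---|---|
| No EoT, ED or follow-up visit | 5, 40, 90 | missing | 0 of 3 | yes |
| ED visit on Day 100 | 5, 40, 90 | Day 100 | 3 of 3 | yes |

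Any one of the three visits is enough, so a non-hysterectomized woman who misses only Visit 7 is unaffected.

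**4. The plan's own figures.** Protocol 8.1 (the figure is a percentage): "The number of completers in Safety Study part after 12 months of treatment is expected to be ~200, anticipating a drop-out rate of 50". Check: 400 × (1 − 0.50) = 200 completers, hence about 200 non-completers. The same section's Efficacy-part figure also reproduces: 300 × 0.65 + 300 × 0.80 = 435. The 50% is drop-out for any reason. The documents do not say how many non-completers would miss all three visits.

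**5. Illustrative size.** Let m be the number of dosed women without a terminal visit and p the true proportion with at least one TEAE, taken as equal in women with and without such a visit. Then

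reported proportion = p × (400 − m)/400, and loss = p × m/400.

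Both m and p are assumptions. Here m = 20, 50 and 100 is 10%, 25% and 50% of 200.

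| m | p = 50% | p = 60% | p = 70% |
|---|---|---|---|
| 20 | 47.5% (−2.5) | 57.0% (−3.0) | 66.5% (−3.5) |
| 50 | 43.75% (−6.25) | 52.5% (−7.5) | 61.25% (−8.75) |
| 100 | 37.5% (−12.5) | 45.0% (−15.0) | 52.5% (−17.5) |

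Worked example: 60% × 380/400 = 57.0%, a loss of 3.0 points.

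**6. The unknown-start gap.** If the start is wholly unknown and the stop date is missing or the event is ongoing, the Table 1 condition cannot be met and 6.2.1.2 does nothing. Compare the partial-date rules in 6.2.1.2: when the known month and year, or the year alone, match treatment start and the stop date is missing, the start is set to Treatment Start Date, which makes the event a TEAE. The two rules take opposite positions on the same uncertainty.

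**The case against.** The strongest reply is that the exclusion is inferred. Nowhere does the SAP say that AEs are dropped when the visit date is missing, and a programmer could well supply a sensible end date. The reason and circumstances of early termination must be documented in the eCRF, and the patient-years formula presupposes an end-of-treatment date for women who have stopped. The table shells and the Efficacy Study part SAP are separate documents and might contain a convention. All this is fair, but it means that a primary endpoint would rest on an unwritten choice in an open-label part, while the written rule gives the wrong answer.

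Three stronger readings are tempting and are not supported.

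- *The women lost left because of AEs.* A reader might infer this from their being non-completers. Protocol 8.3 lists loss to follow-up separately from SAEs, clinical deterioration and endometrial findings. It asks for follow-up of women who stop for a treatment-related AE, and it requires two telephone calls and a registered letter after a missed visit. Many women who leave because of an AE would therefore have a terminal visit.
- *A bias of known size.* A reader might take 20 to 60 women, 40% to 60% of them with an AE, and obtain 8/400 = 2 to 36/400 = 9 points. Neither range has a source in the documents.
- *Events disappear from the report, or discontinuation rates are biased.* All AEs are listed for the Included Set with TEAEs flagged (7.7.1.1), so an unflagged on-treatment event could be seen. Discontinuations and their reasons are tabulated independently of the flag (7.2).

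The unknown-start gap is also narrow. Onset date is required AE information under Protocol 10.4.1, and the partial-date rules already handle most incomplete dates.

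**Conclusion.** The point holds as a defect in the written rule. Table 1 is narrower than Protocol 10.4.1, has no fallback, and is not declared among the changes in SAP Section 8. Followed literally, it removes every dated TEAE of a dosed woman who has no terminal visit and keeps her in the denominator. The direction is certain: reported frequencies can only fall. The size is not known. The figure of 3 points per 20 such women assumes a part of 400, a true TEAE proportion of 60%, and the same proportion in women with and without a terminal visit; only the 400 comes from the documents. The defect does not depend on that illustration. Because it governs the first primary endpoint and is cheap to repair, it should be corrected before the derivation is programmed. The unknown-start gap is secondary and belongs in the same edit.

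**What to change.** In SAP Table 1:

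1. Keep the end-of-treatment, early-discontinuation or follow-up visit as the end of the TEAE window when a woman has one.
2. When she has none, apply no upper limit, so that every AE starting on or after Treatment Start Date is a TEAE.
3. Count an AE with an unknown start and a missing or ongoing stop date as a TEAE, and align the missing-year rule in 6.2.1.2 with this.

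In SAP Section 8, list any difference from the Protocol 10.4.1 definition that remains. One candidate is the strict inequality, which excludes an AE starting on the day of the last visit itself.

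Cost: a few lines of SAP text and a small change to one derivation; no new data are needed. The downside is that a few late events in women without a terminal visit, or a few pre-treatment events with no recorded start, may be counted as TEAEs. For a safety endpoint that is the more acceptable error, and the listings would show which events they are.
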